## 5.4 Other Restrictions and Precautions

### 5.4.1 Prohibited Medications and/or Treatments

Subjects must not undergo any type of facial plastic or reconstructive surgery or cosmetic procedure (e.g., plastic surgery; tissue grafting; tissue augmentation with silicone, fat, or other permanent, semi-permanent, or temporary dermal fillers; neuromodulator injections; or mesotherapy; or ablative procedures) at any time during this study.

The decision to administer a prohibited medication/treatment will be made with the safety of the study participant as the primary consideration. When possible, the Sponsor or the Sponsor's representative should be notified before a prohibited medication/treatment is administered. Prior to attending study visits, subjects must not apply facial cosmetics.

Therapy considered necessary for the subject's welfare may be given at the discretion of the investigator, including but not limited to medications for other conditions (i.e., hypertension, diabetes, etc.), treatment of AEs, estrogens, androgens, anti-androgenic agents, vitamins, iron supplements, folate, and herbal supplements. Medications should be taken consistently throughout the study and at the investigator's discretion.

Concomitant medications as defined for this study include dietary supplements, over-the counter medications, and oral herbal preparations, as well as changes in dosages of current prescription medications. Concomitant medications will be documented for each subject at each scheduled visit. A detailed history of medications will be documented at screening. Subsequently, at each study visit, subjects will be asked what medication, if any, they have taken since the previous visit. All concomitant medications will be recorded on electronic case report forms (eCRFs).

### 5.4.2 Definition of Females of (Non-)Childbearing Potential and/or Acceptable Contraceptive Methods

Women of childbearing potential must have a negative urine pregnancy test before any injections or other treatments are given. A reliable method of contraception must be practiced throughout the study. Women of childbearing potential comprises women who have experienced menarche and who have not undergone successful surgical sterilization (hysterectomy, bilateral salpingectomy, or bilateral oophorectomy) or who are not post-menopausal. The investigator and each subject will determine the appropriate method of contraception for the subject during the participation in the study.

### 5.4.3 Special Diet or Activities

Within the first 24 hours after any filler treatment (HArmonyCa or Juvéderm) subjects should avoid strenuous exercise, extensive sun or heat exposure, and alcoholic beverages. Exposure to any of the above may cause temporary redness, swelling, and/or itching at the injection sites.

## 6 Study Plan and Procedures

### 6.1 Study Subject Number

Subjects who meet all inclusion/exclusion criteria will be assigned a subject enrollment number via the electronic data system that will serve as the subject identification number on all study documents.

### 6.2 Description of Study Days

Study procedures, treatments, and assessments will be performed at the study visits as listed below and as shown in [Table 6.1](#).

**Table 6.1 Schedule of Study Procedures, Treatments, and Assessments**

Study Visit	V0 	V1	V2	V3	V4	V5	V6 	V7 
	Screening	Day 1	Day 30	Day 60	Day 90	Day 120	Day 135	Day 150
Visit window	(Day -14 to Day -1)	N/A	(30 ± 7 days after V1)	(30 ± 7 days after V2)	(30 ± 7 days after V3)	(30 ± 7 days after V4)	(15 + 7 days after V5)	(15 ± 7 days after V6)
STUDY TREATMENTS								
HarmonyCa Injections 		X	X 					
Juvéderm Injections 				X	X	X 		
BOTOX 						X	X 	
STUDY PROCEDURES								
Provide subject information; review/verify study criteria	X							
Informed consent form	X							
Demographics	X							
Medical history	X							
Weight/BMI 	X							X
Pregnancy test 	X	X	X	X	X	X	X 	
Concomitant medications	X	X	X	X	X	X	X	X
2D facial photography	X							X
Standardized digital video	X							X
Adverse events	X	X	X	X	X	X	X	X
Fitzpatrick Skin Phototype	X							
Subject diary		X	X 	X	X	X 		

Study Visit	V0 	V1	V2	V3	V4	V5	V6 	V7 
	Screening	Day 1	Day 30	Day 60	Day 90	Day 120	Day 135	Day 150
Visit window	(Day -14 to Day -1)	N/A	(30 ± 7 days after V1)	(30 ± 7 days after V2)	(30 ± 7 days after V3)	(30 ± 7 days after V4)	(15 + 7 days after V5)	(15 ± 7 days after V6)
STUDY RATING SCALES AND QUESTIONNAIRES								
Self-perception of age (SPA)	X							X
FACE Q 	X							X 
Periorbital aesthetic appearance questionnaire (PAAQ)	X							X
FWS – glabellar lines (GLs)	X							
FWS – crow's feet lines (CFLs)	X							
FWS –forehead lines (FHLs)	X							
Investigator global aesthetic improvement scale (GAIS)								X
Subject GAIS								X

 Screening and Visit 1 can be combined in order to reduce the total number of visits, if judged by the investigator to be appropriate and acceptable for the subject. Identical study procedures will not be repeated where the visits are combined.

 If no BOTOX touch-up is required, the subject will still return for V7.

 All subjects attend V7 for study exit procedures and assessments.

 Prior to attending study visits, subjects must not apply facial cosmetics.

 Juvéderm filler, if required

 BOTOX touch-up if required

 BMI > 30 is exclusionary. Body weight will be measured at screening and end of study (V7) for all subjects. Drastic weight loss or gain may skew assessments of "before" and "after" photos.

 Required for women of childbearing potential

 Pregnancy test not required at V6 if no BOTOX touch-up is needed.

 New subject diary only administered at touch-up if injection occurred. Collect completed diary at the next scheduled visit.

 FACE-Q Scales include Satisfaction with Facial Appearance Scale, Expectations Scale (baseline only), Aging Appraisal, Psychological Function Scale, Social Function Scale, and Satisfaction with Skin Questionnaire.

 FACE-Q Expectations subscale will not be collected at End of Study.

 If HArmonyCa injections are not to be administered to a subject, the subject will begin at Day 1 with V3 study activities (i.e., Juvéderm fillers).

 HArmonyCa touch-up, if required. If not required, proceed with V3 study activities.

### 6.2.1 Study Procedures for Screening Visit (V0)

- Provide subject information; review / verify study criteria.
- Collect ICF.
- Collect subject demographics, including age and gender.
- Collect medical history, including a detailed history of prior cosmetic procedures, with start and stop dates, if applicable, as well as any discontinuations due to intolerance or toxicity.
- Confirm that inclusion/exclusion criteria are met; document status of all washout periods that apply.
- Measure body weight and height and calculate BMI. Body mass index  $> 30 \text{ kg/m}^2$  is exclusionary.
- Perform urine pregnancy test for women of childbearing potential.
- Record concomitant medications.
- Perform 2D facial photography.
- Perform standardized digital video.
- Determine Fitzpatrick Skin Phototype
- Record adverse events (AEs) occurring since signing consent.
- Perform the following study assessments:
  - SPA
  - FACE-Q
  - PAAQ
  - FWS (GLs, CFLs, FHLs)

### 6.2.2 Visit V1 and V2 (HArmonyCa Lidocaine)

Screening Visit (V0) and first study treatment (V1) may occur on the same day if all screening procedures are completed, results received, and all eligibility criteria (inclusion and exclusion) are confirmed prior to treatment administration. But the subject must be in agreement to do this and must have had sufficient time to understand the study, and the investigator also must judge that the subject had enough time to consider the study. It will be a subject and investigator decision together - in the event of any doubt, the subject should not be treated on the same day.

Subjects who have successfully completed screening (V0) will enter the study at V1. If no HArmonyCa will be administered to the subject, please proceed with study activities for V3 as outlined in Section [6.2.3](#) and [Table 6.1](#).

The following activities will be performed at V1 if HArmonyCa Lidocaine is administered:

- Record concomitant medications.
- Perform urine pregnancy test for women of childbearing potential.
- Record AEs.
- Dispense subject diary to record AEs; counsel subject on diary entries that are needed during the next 30 days.
- Perform facial HArmonyCa Lidocaine injections into areas that the subject desires and qualified for per the inclusion/exclusion criteria and within the approved clinical indications (Section 5.1 and Section 5.2, respectively).

At V2, HArmonyCa Lidocaine touch-up treatment may be performed. If touch-up is not performed, please proceed with study activities for V3 as outlined in Section 6.2.3 and Table 6.1. If touch-up for HArmonyCa Lidocaine is performed, perform the following activities:

- Record concomitant medications.
- Perform urine pregnancy test for women of childbearing potential.
- Record AEs.
- Dispense subject diary to record AEs; counsel subject on diary entries that are needed during the next 30 days.
- Perform facial HArmonyCa Lidocaine touch-up injections into areas that the subject desires and qualified for per the inclusion/exclusion criteria and within the approved clinical indications (Section 5.1 and Section 5.2, respectively).

### 6.2.3 Visit V3 and V4 (Juvéderm)

V3 will occur  $30 \pm 7$  days after previous treatment. If HArmonyCa is not given to the subject, the subject may begin with Juvéderm filler injections and V3 activities as outlined in this section and in Table 6.1. If no HArmonyCa is administered, please see guidance regarding screening and first treatment occurring on the same day outlined in Section 6.2.2. V3 and V4 are mandatory regardless of whether further filler treatment is expected. The following study procedures and treatments will be performed at V3 and V4:

- Record concomitant medications.
- Perform urine pregnancy test for women of childbearing potential.
- Record AEs.
- Dispense subject diary to record AEs; counsel subject on diary entries that are needed during the next 30 days
- Perform facial Juvéderm filler injections.

- Facial filler injections (JUVÉDERM VOLBELLA with Lidocaine, and/or JUVÉDERM VOLIFT with Lidocaine, and/or JUVÉDERM VOLUMA with Lidocaine, and/or JUVÉDERM VOLITE [REDACTED] and/or JUVÉDERM VOLUX with Lidocaine) will be administered into areas that the subject desires and qualified for per the inclusion/exclusion criteria and within the approved clinical indications (Section 5.1 and Section 5.2, respectively).

#### **6.2.4 Visit V5 (Juvéderm Touch-up and BOTOX)**

V5 will occur  $30 \pm 7$  days following V4.

- Record concomitant medications.
- Perform urine pregnancy test for women of childbearing potential.
- Record AEs.
- If Filler touch up is given, dispense subject diary to record AEs; counsel subject on diary entries that are needed during the next 30 days
- Administer BOTOX treatment.

#### **6.2.5 Visit V6 (BOTOX Touch-up, if needed)**

V6 will occur  $15 + 7$  days following V5.

- Collect diary from V5, if Filler treatment was given.
- Record concomitant medications.
- Record AEs.
- Perform urine pregnancy test for women of childbearing potential (omit if no BOTOX touch up required at V6).
- Administer touch up BOTOX treatment if needed.

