### 10.3 Injection Site Reactions

Injection site reactions following treatment with dermal fillers include redness, pain after injection, tenderness to touch, firmness, swelling, lumps/bumps, bruising, itching, and discoloration. Subjects will maintain a diary record of the presence, location, frequency, severity, and duration of any ISR for 30 days after each filler treatment.

Subjects will indicate the occurrence of an ISR and severity (none, mild, moderate, severe) of the event. NOTE: ISRs that persist longer than 30 days should be recorded and followed to resolution on the AE eCRF. If an ISR is ongoing or appears after the subject's last study visit, it will be followed up by the sponsor Product Surveillance separate from this study protocol.

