## 10.7 Assessment of Adverse Events

### 10.7.1 Severity

Assessment of severity of an AE will be rated according to the definitions in [Table 10.1](#) and the worst grade documented. The investigator will review these [definitions](#) with the subject for use when completing the subject diary. For events reported on the AE eCRF, e.g., ISRs that persist beyond the diary period and other AEs, the investigator will determine the severity classification based on these definitions, his/her experience in the use of dermal fillers and/or the subject's description of the event.

The term “severe” is used to describe the intensity of an AE; the event itself could be of relatively minor clinical significance (e.g., “severe headache”). This is not the same as “serious.” Seriousness of AEs is based on the outcome of an AE and usually associated with events that pose a threat to a subject’s life or functioning.

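### The 30-day injection site reaction diary after a V5 filler touch-up is collected at V6, 15 to 22 days after V5, and SAP 9.5 has no rule for a reaction still present at the last entry

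*Protocol*

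**What the plan says.** **Diary length.** Protocol 6.2.4 has sites dispense a diary when a filler touch-up is given at V5 and "counsel subject on diary entries that are needed during the next 30 days". Protocol 10.3 sets the general rule: "Subjects will maintain a diary record of the presence, location, frequency, severity, and duration of any ISR for 30 days after each filler treatment". SAP 9.5 repeats the 30 days and makes no exception for V5.

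**Collection.** Protocol 6.2.5 lists, at V6, "Collect diary from V5, if Filler treatment was given". Table 6.1 footnote 10 asks for the completed diary at the next scheduled visit, which after V5 is V6. Table 6.1 puts V6 at "15 + 7 days after V5", and 6.2.5 gives the same window.

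**The other filler diaries.** The visits after V1 to V4 are each 30 ± 7 days later. For example, a diary for a V2 touch-up is collected at V3, scheduled "30 ± 7 days after V2".

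**Analysis.** SAP 9.5 computes the duration of each symptom as the last minus the first occurrence date in the eDiary, plus 1. It summarises this by visit, with categories 1-3, 4-7, 8-14 and 15-30 days, and tabulates ISRs by visit, symptom and maximum severity. It says nothing about a symptom still present at the last entry or a diary shorter than 30 days.

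**The concern.** A site that follows 6.2.5 literally cannot collect a finished 30-day diary. V5 is the only filler visit at which the nominal schedule itself cuts the diary short. At the other visits a shortfall arises only at the early edge of the window.

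The SAP formula does not distinguish an ISR that stopped from one whose recording stopped. A truncated ISR is therefore tabulated as completed, and the error runs one way, towards shorter durations. In the by-visit summary, the V5 results would stand next to V1 to V4 results that were observed for longer, with nothing to signal the difference. An ISR that begins or worsens after V6 would also be missing from the diary-based severity table. ISRs are a named safety endpoint in SAP 3.3, and 9.5 is the section that summarises them.

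**Working it through.** **Inputs.** Diary period 30 days (Protocol 6.2.4 and 10.3, SAP 9.5). V6 at 15 to 22 days after V5, and V7 at 15 ± 7 days, that is 8 to 22 days, after V6 (Protocol Table 6.1). Visits after V1 to V4 at 30 ± 7 days (Table 6.1). Duration formula and categories from SAP 9.5.

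**Check of the schedule.** The nominal days are 120 for V5, 135 for V6 and 150 for V7. So V6 − V5 = 135 − 120 = 15 days, which agrees with the stated window, and V7 − V5 = 150 − 120 = 30 days.

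**Convention.** Day 0 is the V5 injection and diary days are 1 to 30. These are days after V5, not study days. Collection is on Day v, and entry is assumed to stop then.

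**Diary days not recorded = 30 − v**

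| Collection | v | Days not recorded | Share of 30 |
|---|---|---|---|
| V6, earliest | 15 | 15 | 50% |
| V6, latest | 22 | 8 | 27% |
| V1 to V4 diaries, earliest next visit | 23 | 7 | 23% |
| V1 to V4 diaries, nominal next visit | 30 | 0 | 0% |

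**Effect on duration.** Take an ISR with onset on Day d that is still present at v and ends on Day e, with v < e ≤ 30.

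- Recorded duration = v − d + 1.
- True duration = e − d + 1.
- Shortfall = e − v, which is 1 to 15 days for v = 15 and 1 to 8 days for v = 22.

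**Effect on the categories**

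- v = 15, d = 1: recorded 15 − 1 + 1 = 15, so the ISR stays in 15-30.
- v = 15, d = 2: recorded 15 − 2 + 1 = 14 (category 8-14). The true duration is 15 (e = 16) to 29 (e = 30), category 15-30.
- v = 22, d = 1: recorded 22, so the category does not change.
- v = 22, d = 9: recorded 22 − 9 + 1 = 14 (category 8-14). The true duration is 15 (e = 23) to 22 (e = 30), category 15-30.

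For an ISR that starts early, the mean and median are affected before the category is.

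**If collection moved to V7.** V7 falls from 15 + 8 = 23 to 22 + 22 = 44 days after V5, nominally 30. The largest loss would be 30 − 23 = 7 days, the same as for the other filler diaries.

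**The case against.** **Entry may not stop at collection.** No passage says that it does. The SAP speaks of an eDiary, and footnote 10 speaks of a completed diary. This stands: every loss figure above is conditional on it. Against it, no passage provides for a later collection of the V5 diary.

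**V6 may not take place.** Footnote 2 says "If no BOTOX touch-up is required, the subject will still return for V7", which can be read as going straight to V7, while footnote 9 and 6.2.5 suggest that V6 is still held. If the subject goes straight to V7 at its scheduled time, at most 7 days are lost. This also stands.

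**A reader might infer that ISRs between V6 and Day 30 go unrecorded altogether.** Protocol 10.3, read alone, invites this: "ISRs that persist longer than 30 days should be recorded and followed to resolution on the AE eCRF". Protocol 10.7.1 uses a different limit, "ISRs that persist beyond the diary period and other AEs". But Protocol 4.3 collects AEs, including ISRs, through V7. Section 10 and 10.7.3 put AEs on the eCRF, 6.2.6 records AEs at V7, and 6.2.7 has ISRs solicited and recorded at every return to the site. The information has a route; it does not enter the SAP 9.5 formula, which uses eDiary dates only.

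**A reader might read the absence of a diary step in the V7 list (6.2.6) as proof that nothing is collected there.** That is weak evidence, because the V1 to V5 lists have no collection step either. The explicit V6 instruction in 6.2.5 carries the point.

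**A reader might compute a larger loss from the SAP schedule**, whose first header gives V6 as 15 ± 7 days. Protocol Table 6.1, Protocol 6.2.5 and the continuation header of the same SAP table all give 15 + 7. The single outlier supports a consistency edit, not a wider range of loss.

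**A rule may exist elsewhere.** SAP 1.0 places table specifications in a separate document, which was not available. The supportable statement is that SAP 9.5 itself states no rule and points to none.

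**Conclusion.** The documents contradict themselves: a 30-day diary is required after a V5 filler touch-up, and its collection is set at 15 to 22 days. If V6 is attended and entry stops at collection, 8 to 15 of the 30 days (27% to 50%) are not recorded. Under SAP 9.5, an ISR still present at that point is then reported as ended, up to 15 days too short if it ends by Day 30.

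The consequence is small. It is confined to the diary-based descriptive duration and severity summaries for V5 touch-ups, and it arises only if ISRs are present after V6. The documents do not give the number of such touch-ups or the persistence of ISRs. No tested endpoint is affected, and the text does not support a claim that ISR safety information after V6 is lost. Severity: minor.

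**What to change.** 1. **Protocol.** Reconcile 6.2.4, 6.2.5, 10.3 and Table 6.1 footnote 10 so that the V5 diary is reviewed at V6, continued, and collected at V7 (23 to 44 days after V5, nominally 30). Footnote 3 already has all subjects attend V7, so no visit is added, and diary coverage would no longer depend on whether V6 is held.
2. **SAP 9.5.** Report an ISR present on the last diary day in its own row as ongoing at diary collection, not as a completed duration. Report diary days observed by visit (n, median, minimum, maximum). This also covers V1 to V4 diaries collected early. It needs a last-entry or collection date. If neither is in the data, the date of the next attended visit can serve as a labelled proxy.

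The cost is a few lines in the protocol and one paragraph in the SAP. SAP 13.0 records that version 1.1 already revised the ISR summaries in light of collected data; for diaries already collected, only step 2 applies.

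**Minor consistency edits.** Correct the first V6 header in the SAP schedule from 15 ± 7 to 15 + 7, to agree with its continuation header and the protocol. In the SAP duration categories for treatment-emergent AEs (the section 9.2.1 headed by SOC, PT and severity), change ≥ 30 days to > 30 days, because a 30-day event now falls in two categories.

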#### **6.2.6 Visit V7 (Final Study Visit)**

V7 will occur  $15 \pm 7$  days following V6.

- Measure body weight and calculate BMI.
- Record concomitant medications.
- Perform 2D facial photography.
- Perform standardized digital video.
- Record AEs.

- Perform the following study assessments for all subjects:
  - SPA
  - PAAQ
  - FACE-Q (except for Expectations subscale)
  - Investigator GAIS
  - Subject GAIS

If a subject discontinues the study before V7, the subject will be asked to have this final study visit for collecting all clinical data required during this visit.

#### **6.2.7 Unscheduled/Missed Visits**

Each time the subject returns to the study site, the investigator (or designee) will solicit and record information about ISRs, other AEs, and concomitant medications. An interim or unscheduled visit may replace a scheduled visit if it occurs within the acceptable time window for a scheduled visit or if the scheduled visit was missed. All applicable procedures should be performed.

## 7 Methods of Assessment and Endpoints

### 7.1 Clinical Scales for Treatment Inclusion Only

- Investigator's assessment of the severity of GLs at maximum frown using the FWS with photonumeric guide ([Appendix 10](#))
- Investigator's assessment of the severity of CFLs at maximum smile using the FWS with photonumeric guide ([Appendix 11](#))
- Investigator's assessment of the severity of FHLs at maximum eyebrow elevation using the FWS with photonumeric guide ([Appendix 12](#))
- Subject's assessment of expectations of life change as measured by the FACE-Q Expectations Scale ([Appendix 3](#))

### 7.2 Efficacy Endpoint Measurements

#### 7.2.1 FACE-Q

- Subject's assessment overall facial appearance as measured by the FACE-Q Satisfaction with Facial Appearance Scale ([Appendix 2](#))
- Subject's assessment of age-related facial appearance as measured by the FACE-Q Aging Appraisal ([Appendix 4](#))
- Subject's assessment of psychological well-being as measured by the FACE-Q Psychological Function Scale ([Appendix 5](#))
- Subject's assessment of social function as measured by the FACE-Q Social Function Scale ([Appendix 6](#))
- Subject's assessment of overall satisfaction with skin as measured by the FACE-Q Satisfaction with Skin Questionnaire ([Appendix 7](#))

#### 7.2.2 Self-Perception of Age Questionnaire

- Subject's assessment of age-related facial appearance as measured by the SPA Questionnaire ([Appendix 1](#))

#### 7.2.3 Global Aesthetic Improvement Scale

- Investigator's assessment of global facial aesthetic improvement as measured by the 5-point GAIS ([Appendix 13](#))
- Subject's assessment of global facial aesthetic improvement as measured by the 5-point GAIS ([Appendix 13](#))

